3. TREATMENT

All eligible study participants will self-administer active tvCVS treatments twice daily with the TNMTM Generation 4.0 Device during the first 112 days of the OLE (days 113-197 in the study protocol) and the last 56 days of the OLE (days 309-365 in the study protocol). There will be no treatments administered between the end of treatment 1 (EOT1) clinic visit on day 197 and the follow up 3 (FU3) clinic-visit on day 309.

4. SAMPLE SIZE DETERMINATION

Any of the 184 participants who randomize in the RCT and complete the RCT portion of the study will be eligible to participate in the OLE if they are able to consent to the OLE portion of the study. It is expected that approximately 166 participants (83 per RCT randomized group) will complete the RCT, and that there will be an additional 10% attrition. As a result, it is expected that 74 participants will make up the passive-active treatment group. This number is sufficient to detect a difference of 2.64 points in the MDS-UPDRS Part I total score for the null hypothesis that mean change scores for the passive-active treatment group at EOT1 in the OLE is equal to the mean change score of the passive-active treatment group at EOT1 in the OLE represents greater symptomatic improvement than that of the passive treatment group at the end of the RCT with a power of >98% given a mean difference of -2.64 and a standard deviation of 5.32 points and alpha of 0.05 for a paired t-test. Following the argument given in the RCT SAP (Appendix 1), this implies that the sample size should be sufficient to adequately power the highly correlated⁸ endpoint of MDS-NMS.

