9.1 Sample Size Determination

The sample size for this study was set to achieve > 90% power to detect the minimal clinically important difference (MCID) of -2.64 points in the MDS-UPDRS: Part I⁶⁰. The estimated group sample sizes of 83 and 83 (166 total) to complete assumes a rate of attrition of 10% during the RCT and was set to achieve 89% power to detect a difference of -2.64 points in the MDS-UPDRS Part I total score between the null hypothesis that both group average change scores are equal and the alternative hypothesis that the average change score of the treatment group is -2.64 points less than that of the passive treatment group with estimated within group standard deviation of 5.32 points and with a 2-sided significance level (alpha) of 0.05. Competitive enrollment will close once 184 participants have been randomized into the RCT. This number allows for the maintenance of 89% power to detect the estimated MCID at the end of the RCT and at the end of the first treatment period in the OLE assuming 10% attrition during each of those two periods.

Note that the primary endpoint is the MDS-NMS, not the MDS-UPDRS: Part I. However, the two scales are highly correlated ($r_s=0.75$)¹, and the MDS-UPDRS: Part I has a pre-established MCID⁵⁹ whereas the MDS-NMS does not. The sample size (184 to randomize), derived from the MDS-UPDRS: Part I achieves >90% power to detect the estimated MCID of -35 points in the MDS-NMS. Participants will continue to be enrolled in the RCT until at least 184 participants have randomized, and if there are additional participant withdrawals, they will not be replaced. Participants who have entered the baseline period but have not yet randomized when the competitive enrollment target is achieved may be withdrawn from the study prior to randomization and, as a result, would not be included in any of the analyses. Data from all randomized study participants will be evaluated for analyses of safety and efficacy.

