7.2. HANDLING DEPENDENT OBSERVATIONS

Due to the design of the OLE, a participant may have received treatment in a crossover nature. For those participants, special data handling methods are required. For the passive-active group, assessments will be assigned to the treatment received at the time of the given assessment. All observations captured up to the first treatment with active tvCVS will be assigned to the passive treatment. All observations at or after the first treatment with active tvCVS will be assigned to the active treatment.

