7.8. EFFICACY ANALYSIS

⁷Analysis of continuous endpoints will be conducted utilizing the methodology as described in section 7.7 of the SAP v6.0 for RCT Study (Appendix 1). For comparisons within the passive-active arm, the visit variable will be based on the adjusted analysis visit for the active comparisons and the subject effect of the model will be nested within ARM to account for the crossover nature of these data. For efficacy endpoints that have a baseline defined, only participants who have baseline data collected for the endpoints will be included in efficacy analyses.

7.8.1. Primary Objectives:

The primary objective is to further evaluate the effectiveness of TNM[™] Device treatments to reduce non-motor symptom burden in PD for the purposes of supporting reimbursement and clinical adoption.

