7.8.2. Primary Endpoint and Comparison of Interest

The primary endpoint is the change in MDS-NMS total score at the end of treatment. The primary comparison is its change in MDS-NMS total score during the RCT treatment period (days 29-113) versus the change in MDS-NMS total score during the OLE treatment period 1 (days 113-197). This analysis of the primary comparison will only utilize the passive-active treatment group. The analysis will utilize data obtained during the RCT as well as data obtained from the OLE baseline and the twelve weeks of the OLE in which the participants will have been given the intervention.

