4. SAMPLE SIZE DETERMINATION

The sample size for this study was set to achieve ~ 90% power to detect a minimal clinically important difference (MCID) of -2.64 points in the MDS-UPDRS: Part I (Horvath, Aschermann et al. 2017) for both the RCT and the first treatment period during the OLE. This estimated group sample sizes of 83 and 83 (166 total) to complete the RCT (assuming 10% attrition) achieves 89.2% power to detect a difference of 2.64 points in the MDS-UPDRS Part I total score for the null hypothesis that both group average change scores are equal and the alternative hypothesis that the average change score of the active treatment group represents greater symptomatic improvement than that of the passive treatment group given an estimated within group standard deviation of 5.32 points and a 2-sided significance level (alpha) of 0.05.

This sample size also achieves > 90% power to evaluate the primary endpoint of the STEM-PD OLE (see the STEM-PD OLE SAP for additional details).

Note that the primary outcome measure for the STEM-PD RCT is the MDS-NMS, not the MDS-UPDRS: Part I. However, the two scales are highly correlated (correlation coefficients = 0.75-0.85) (Chaudhuri, Schrag et al. 2019, van Wamelen, Martinez-Martin et al. 2021), and the MDS-UPDRS Part I has a pre-established MCID whereas the MDS-NMS does not. Given the high correlation reported for these two outcome measures in previous studies, an analysis was performed to estimate the MCID for the MDS-NMS. The MCID for the MDS-UPDRS: Part I is

2.64 points (Horvath, Aschermann et al. 2017). Since the estimated standard deviation of the MDS-UPDRS Part I for this study is 5.32 points, the MCID represents 49.6% of the standard deviation.

The standard deviation of the MDS-NMS scale has been reported as 65.87 points (Chaudhuri 2020). Using the same proportion of the standard deviation, the estimated MCID for the MDS-NMS scale for this study would be 32.7 points. Additionally, in an unpublished study analysis of participants from the original validation study, Martinez-Martin determined that among a cohort with MDS-UPDRS Part I scores greater than 10, which approximates the inclusion criterion for this study, the standard deviation of the MDS-NMS was 70.8 points. Utilizing a definition of 49.6% of the standard deviation, based upon the Martinez-Martin study, the MCID for the MDS-NMS scale would be 35.1 points.

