7.7. EFFICACY ANALYSIS

Efficacy will be determined using (Zeger and Liang 1992, Zorn 2001) a linear regression utilizing a mixed effects (i.e., mixed model repeated measures [MMRM]). This approach allows for repeated measurements on a subject (i.e., all time points during the study) and unequally spaced as well as missing data (dropouts or intermittent), allows for the inclusion of continuous or categorical covariates, allows for a flexible specification of the covariance structure. This modeling technique has been shown to produce unbiased estimates in the case of data missing at random. Additionally, the MMRM estimation is robust to departures from normality. (Rubin 1987)

The following MMRM model (Zeger and Liang 1992, Zorn 2001) will be analyzed to determine significance for the primary endpoint:

$$\begin{split} Y_{ij} &\sim N(0, \sigma^2) \\ Y_{ij} &= \beta_0 + \beta_1 * ARM_i + \beta_2 * VISIT_{ij} + \beta_3 * ARM_i * VISIT_{ij} + \beta_4 * SITE_i \\ & \text{where:} \end{split}$$

 $Y_{ij} = (MDS_NMS \text{ total score for participant i at time } j) - (MDS_NMS \text{ total score for})$

participant i at baseline),

 $ARM_i = 1$ if participant i is in the treatment arm

= 0 if participant i is in the passive arm,

 $VISIT_{ij}$ = an ordinal variable representing the visit for j^{th} measurement for

participant i

SITE_i is a nominal variable indicating the site for participant i,

An unstructured covariance structure will be utilized for the R matrix. The Kenward-Roger approximation will be used to estimate the denominator degrees of freedom. The difference between active and passive treatment at each visit will be estimated based on the Least Squares Mean (LSMean) difference between the treatment groups at the visit from the MMRM with the associated 90% confidence interval (CI) and 1-sided P-value. Additionally, the p-value for the site effect will be presented. If the unstructured covariance matrix results in convergence issue, the heterogeneous Toeplitz covariance structure followed by the heterogeneous first-order autoregressive (AR(1)) structure will be used. In these cases, sandwich estimators will be obtained from the model fitting procedure to ensure unbiased estimation of the treatment effect.

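### The OLE's >98% power uses the RCT's within-group SD of 5.32 as the SD of a paired difference, disagrees with the Protocol's 89%, and assumes pairing that the model wording does not secure

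*SAP*

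**What the plan says.** OLE SAP section 4 expects 83 passive-arm participants to complete the RCT and, after a further 10% attrition, 74 in the passive-active group. It then claims "power of >98% given a mean difference of -2.64 and a standard deviation of 5.32 points and alpha of 0.05 for a paired t-test", for MDS-UPDRS Part I as a stand-in for the MDS-NMS. It does not say whether alpha is one- or two-sided. OLE SAP 7.8.2.1 tests the primary endpoint one-tailed at 0.05, while the general default in OLE SAP 7.1 is two-sided.

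RCT SAP section 4 obtains 89.2% power for the two-arm comparison of change scores "given an estimated within group standard deviation of 5.32 points". Protocol 9.1 describes 5.32 in the same way.

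Three figures are given for power at the end of the first OLE treatment period:
- Protocol 9.1: "maintenance of 89% power to detect the estimated MCID at the end of the RCT and at the end of the first treatment period" of the OLE.
- RCT SAP section 4: "This sample size also achieves > 90% power to evaluate the primary endpoint of the STEM-PD OLE".
- OLE SAP section 4: >98%.

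The OLE primary comparison sets the change over days 29–113 against the change over days 113–197 (OLE SAP 7.8.2), and "This analysis of the primary comparison will only utilize the passive-active treatment group". OLE SAP 7.4 makes the RCT end-of-treatment value the OLE baseline. On modelling, OLE SAP 7.8 says "the subject effect of the model will be nested within ARM to account for the crossover nature of these data". OLE SAP 7.2 says that, for this group, "assessments will be assigned to the treatment received at the time of the given assessment". The parent model in RCT SAP 7.7 codes ARM as treatment versus passive and adds: "An unstructured covariance structure will be utilized for the R matrix".

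**The concern.** One number is made to serve two different quantities. In the RCT, 5.32 is the spread of a single change score within an arm. In a paired t-test the relevant SD is that of the within-person difference between two change scores, which depends on how those two changes correlate. The plan gives no correlation, and the design argues against the one needed: a high score at day 113 makes the first change look worse and the second look better.

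The model wording raises a related problem. The sizing relies on pairing. If the two periods of one person are fitted as separate subjects, the covariance between them is dropped. With negative ρ, dropping it makes the standard error too small and the primary p-value too small. The secondary hierarchy in OLE SAP 7.8.4 starts from that p-value.

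**Working it through.** **Inputs.** n = 74, difference 2.64, SD 5.32 (OLE SAP 4). 83 per arm, 5.32 as within-group SD, two-sided 0.05 (RCT SAP 4). One-sided 0.05 for the OLE primary test (OLE SAP 7.8.2.1). The correlation ρ between the two changes is not in the documents and is an assumption throughout. Both changes are taken to have SD 5.32.

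**1. Reproduce the plan's figures.** Paired t-test, noncentral t with 73 df and noncentrality 2.64·√74/5.32 = 4.27: 98.8% two-sided, 99.5% one-sided. So >98% follows from its own inputs. RCT, normal approximation: 2.64/(5.32·√(2/83)) − 1.96 = 3.197 − 1.960 = 1.237, giving 89.2%, the RCT SAP figure. In the RCT, therefore, 5.32 acts as the within-group SD of one change.

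**2. SD of the paired difference.** Var(D) = 2·5.32²·(1−ρ), so SD(D) = 5.32·√(2(1−ρ)).

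| ρ | SD(D) | Power, one-sided 0.05 | Power, two-sided 0.05 |
|---|---|---|---|
| +0.5 | 5.32 | 99.5% | 98.8% |
| 0 | 7.52 | 91% | 85% |
| −0.25 | 8.41 | 85% | 76% |
| −0.5 | 9.21 | 79% | 68% |

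Reaching 98% needs ρ above about +0.35 one-sided or +0.45 two-sided. Reaching 90% needs ρ above −0.04 or +0.16. The Protocol's 89% corresponds to ρ of about −0.08 one-sided.

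**3. Likely sign of ρ.** The changes are Y113 − Y29 and Y197 − Y113. With equal variances and equal visit correlation r, each has variance 2(1−r) and their covariance is r − 1 − r + r = −(1−r), so ρ = −0.5 whatever r is. With the mean of days 0 and 29 as baseline (RCT SAP 7.7.1), ρ is about −0.58. If correlation decays over time (AR(1), r per 84 days, single baseline), ρ = −(1−r)/2: −0.25 at r = 0.5 and −0.10 at r = 0.8.

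**4. Could 5.32 be a cross-sectional score SD?** Then, with equal visit correlations, the change SD is 5.32·√(2(1−r)) and the paired-difference SD is 5.32·√(6(1−r)).

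| r | RCT power, two-sided | OLE power, one-sided | OLE power, two-sided |
|---|---|---|---|
| 0.5 | 89.2% | 79% | 68% |
| 0.80 | 99.9% | 98.7% | 97.0% |
| 0.83 | 99.98% | 99.5% | 98.7% |

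No single r in this structure returns both the RCT's 89.2% and the OLE's >98%.

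**5. Subject nested within ARM.** The comparison uses only the passive-active group, so the randomised arm is constant and cannot carry the treatment contrast. Given the assignment rule in OLE SAP 7.2 and the coding in RCT SAP 7.7, ARM must denote the treatment period. Subject-within-ARM then ordinarily gives each person two independent blocks. The assumed variance of the contrast is V1 + V2; the true one is V1 + V2 − 2Cov. Type I error at nominal one-sided 5% is P(Z > 1.645·√[(V1+V2)/(V1+V2−2Cov)]). Example with a single baseline and independent visits: V1 = V2 = 2, Cov = −1, ratio √(4/6) = 0.816, P(Z > 1.343) = 9.0%.

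| Correlation per 84 days (AR(1)) | Single day-29 baseline | Two-visit baseline (days 0 and 29) |
|---|---|---|
| 0 | 9.0% | 9.5% |
| 0.5 | 7.1% | 7.3% |
| 0.8 | 5.8% | 5.9% |

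Simulation (40,000 runs per case) gave 9.1%, 7.1%, 5.8% and 9.5%, 7.1%, 5.9%; a paired test stayed at 4.9–5.1%.

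**The case against.** The >98% is not a miscalculation: it reproduces, and in a sentence about a paired t-test an SD ordinarily means that of the paired difference. That is right as far as it goes. The fault lies in an input with no source whose value coincides with an SD defined for something else.

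The replacement range is not the plan's either. No visit correlation is given, and the result depends on the assumed structure: AR(1) at 0.8 per 84 days gives ρ = −0.10 and 89% one-sided, so 79% is the pessimistic end. Strong person-specific trends could even make ρ positive. This stands, and the figures are a range rather than a corrected power. But none of the visit-correlation structures examined comes near +0.5.

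The three power figures can be partly reconciled. A power above 98% is also above 90%, and the Protocol's 89% may be meant as a floor. Protocol 9.1 does not name the OLE test, and Protocol section 3 defers OLE evaluation to the OLE SAP. The figures may therefore not strictly contradict one another, but three different values for one time point still need reconciling.

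On nesting, the sentence in OLE SAP 7.8 states that its purpose is to handle the crossover, and it also uses the word arm for the randomised cohort. If ARM were the cohort, each person would keep one block. But the cohort is constant in this analysis, so that reading leaves no treatment term. The intent may well be right; the wording does not deliver it. The Type I error figures also leave out interim visits, site and the conditional baseline covariate, and their upper end assumes uncorrelated visits, which is unlikely for a chronic-disease score.

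**Conclusion.** The concern holds. The >98% requires a correlation of +0.5 between the two changes if 5.32 is the SD of each, as in the RCT calculation. The plan neither states nor supports that, and the shared day-113 score points the other way. For ρ from 0 to −0.5 the power is 91% to 79% one-sided. This assumes equal SDs for the two changes and a correlation range that the documents do not supply.

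The nested wording does not specify the paired analysis on which the sizing rests. Fitted literally with negative ρ, it gives a one-sided error of roughly 5.8% to 9.5% under the visit correlations assumed here. With positive ρ it would be conservative.

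This should be fixed before analysis. It does not alter the number of participants, which follows from RCT completion.

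**What to change.** 1. In OLE SAP section 4, state the SD of the within-person difference between the two change scores with its source, or give a range for ρ. Restate the power with its sidedness, for example 91% to 79% one-sided for ρ from 0 to −0.5.
2. Align the OLE power statements in Protocol 9.1 and RCT SAP section 4 with that figure.
3. In OLE SAP 7.8, define ARM and replace the nesting phrase with one unstructured covariance block per participant spanning both periods. Alternatively, test the within-person contrast (Y197 − Y113) − (Y113 − baseline), with baseline as defined in RCT SAP 7.7.1.

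The cost is wording and a less favourable stated power. No additional participants or data are needed.

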5. INTERIM ANALYSIS

No interim analysis is planned for the OLE.

6. INDEPENDENT DATA MONITORING

The TNMTM Device has been designated as a Non-Significant Risk Device for use in this study population. However, the Sponsor has chosen to implement an Independent Medical Monitor (IMM) for the preceding RCT and the OLE to provide independent safety monitoring and to confirm data integrity. The IMM is a physician with extensive experience in Parkinson's disease and clinical trials and has no perceived or real conflict of interest with the Sponsor or in the study outcomes. The IMM will review the research protocol and ongoing study activities with emphasis on data integrity, protocol adherence and study participant safety issues while making recommendations to the continuation, modification or conclusion of the trial. The IMM will review data at least four times per year during the RCT and OLE studies.

The Sponsor will also ensure critical safety and data points will be monitored per the STEM-PD Clinical Monitoring Plan (CMP) and the STEM-PD Data and Safety Management Plan (DSMP). A summary of key monitoring procedures is noted below:

Each site will be assigned a Clinical Research Associate (CRA) who will monitor the data to ensure the protection of rights and safety of human subjects, to verify the reported trial data are accurate, complete, and verifiable from source documents, and that the trial is conducted in compliance with the currently approved protocol/amendment(s), with Good Clinical Practice and with the applicable regulatory requirements. For all enrolled study participants, 100% source data review (SDR) and source data verification (SDV), where applicable, will occur of informed consent documents and process, inclusion and exclusion criteria, primary endpoints and key secondary endpoints (e.g., MDS-UPDRS Part III and CGI-I), all protocol deviations and safety reports, including adverse events and safety endpoints. Targeted source data verification will occur for all other endpoints per the Targeted Source Data Verification (TSDV) portion of the CMP. Review of study-wide trends and key risk indicator (KRI) metrics will be reviewed in a departmental meeting to occur at least once a month. If trends are identified, the Sponsor will review with the study-assigned medical monitor and implement a Correction and Preventative Action (CAPA) Plan. The study-specific Medical and Safety monitor, who has extensive experience with the device, will review and sign off on all AEs at least monthly, and all Unanticipated Adverse Device Effects (UADE) within 2 days of acknowledgment of the event. All UADEs will be reported to the ethics committees and all site Investigators per the protocol and regulatory requirements.

Previous studies with the Device have not reported any Serious Adverse Device Effects (SADEs) or UADEs. As none are anticipated for this study, if two or more serious and related adverse events (SADE or UADE) are reported, the study will pause while universality and unblinded review occurs by the Medical and Safety monitor. Additionally, the IMM is providing additional oversite for this study, and she/he will review these events for adjudication and agreement and will provide recommendations to the Sponsor.

7. STATISTICAL METHODS

7.1. GENERAL METHODS

Descriptive statistical methods will be used to summarize the data from this study, with formal hypothesis testing performed for the primary and key secondary efficacy endpoints. Unless stated

otherwise, the term "descriptive statistics" refers to number of participants, mean, median, standard deviation, minimum, and maximum for continuous data, and frequencies and percentages for categorical data. For categorical variables, the denominator of percentages will be the number of subjects in the treatment group, except for those collected by study visit and/or scheduled time point, in which case the denominator of percentages will be the number of subjects with a non-missing value at the visit and/or the scheduled time point.

All data collected during the study will be included in data listings. Unless otherwise noted, the data will be sorted first by RCT treatment group, subject number, and then by date within each subject number.

All statistical testing will be two-sided and will be performed using a significance (alpha) level of 0.05 unless otherwise specified. P-values will be presented to three decimal places. For exploratory endpoints, inferential analyses including 95% confidence intervals and p-values will be provided, and no statements about statistical significance will be made. The p-values will be provided as informational only.

The statistical analyses may be conducted with the SAS® software package version 9.4 or higher or with GraphPad Prism software version 9.3.1 or higher.

